4 DETERMINATION OF SAMPLE SIZE

Sample size calculation was performed using the nQuery+nterim version 4.0 statistical software. Based on a review of comparable clinical literature ([2-8]), it is assumed for this power calculation that a change of 3.8 cm on a 10-cm VAS represents a clinically meaningful difference in pain as experienced between lidocaine-treated and non-lidocaine-treated NLFs. Assuming a statistical power, $1-\beta$ of 95%, a one-sided level of significance of $\alpha = 0.025$, and a conservative estimate of standard deviation of difference of 7, a total of 47 subjects will be required to be enrolled into the trial. In order to accommodate likelihood of potential subject dropout after randomization and prior to treatment (up to 10% attrition), a total of 52 subjects will be enrolled, yielding approximately 104 total NLFs (52 Test and 52 Control). Additionally, a minimum of 20% of the enrolled total sample size will consist of subjects in the Fitzpatrick Skin Types IV, V, or VI group. Subjects from the Fitzpatrick skin type IV, V, and VI group will be approximately evenly distributed within the IV, V, and VI categories.

5 ANALYSIS SETS

The following analysis sets will be defined for the statistical analysis of this clinical study:

Safety Evaluation Set (SES)

The Safety Evaluation Set (SES) will comprise subjects who are enrolled into the study, randomized, and receive an injection.

Full Analysis Set (FAS)

The Full Analysis Set (FAS) will consist of all randomized subjects and will be analyzed as randomized. This will be the primary population used for the efficacy analyses..

Per Protocol Set (PPS)

The Per Protocol Set (PPS) is a subset of subjects in the FAS without major protocol deviations. Final determination of what constitutes major or minor protocol deviations will be made prior to database lock during the Blinded Data Review Meeting (BDRM).

6 ENDPOINTS FOR ANALYSIS

6.1 Effectiveness Endpoints

6.1.1 *Primary Effectiveness Endpoint*

The primary effectiveness endpoint is the pain, measured using a 10-cm visual analogue scale (VAS), immediately after split-face NLF treatment (i.e., at time zero) on Day 1. Time zero is defined as the time the last injection needle is removed from each NLF, separately, after a full correction on Day 1.

6.1.2 *Secondary Effectiveness Endpoint*

The secondary effectiveness endpoint is the response according to the Merz NLF Scale for each NLF as assessed live by the blinded evaluator at Week 6. Response is defined as ≥ 1 -point improvement on the Merz NLF Scale for each NLF compared to baseline. Each NLF is to be assessed separately. The blinded evaluator is a qualified healthcare practitioner, delegated by the treating investigator.

[REDACTED]

[REDACTED]

[REDACTED]

[REDACTED]

[REDACTED]

[REDACTED]

- [REDACTED]
- [REDACTED]
- [REDACTED]
- [REDACTED]

6.2 Safety Endpoints

- Incidence and nature of device- and/or injection-related AEs and SAEs observed during the study.
- Incidence, severity, and duration of pre-specified CTRs reported in subject diaries.

7 STATISTICAL ANALYSIS METHODS

Continuous variables (values and changes from baseline) will be summarized by n, mean, standard deviation, median, minimum, and maximum. For qualitative variables, absolute and percent frequencies (n, %) will be displayed. Confidence limits and p-values will be given, where appropriate.

P-values when presented will be reported to four decimal places (e.g. p=0.0375). P-values below 0.0001 will be presented as '<0.0001'.

Minimum and maximum will be reported to the same number of decimal places as the data were collected; mean and median will be reported to one decimal place greater than the data were collected, and standard deviation to two decimal places greater. For derived data an adequate number of decimals will be chosen. Percentages will be calculated using the denominator of all subjects in a specified population or treatment group with available (non-missing) value of the variables in question. The denominator will be specified in a footnote to the tables for clarification if necessary. Percentages will be reported to one decimal place.

7.1 Effectiveness Variables

The analysis of the primary and the secondary effectiveness variables will be based primarily on the FAS and additionally, for sensitivity purposes, on the PPS. All other effectiveness variables will be analyzed based on the FAS. Statistical tests will be two-sided at $\alpha = 0.05$

except for the primary effectiveness analysis where a one-sided $\alpha = 0.025$ will be used. Two-sided confidence limits (95%) and p-values associated with the appropriate test statistic will be provided where necessary.

7.1.1 Primary Effectiveness Variable

The analysis of the reduction in pain, measured using a 10-cm VAS, in the Test NLF compared to the Control NLF at time zero will be performed using a paired t-test to test the one-sided hypothesis that the mean of the differences in VAS scores between Test (μ_T) and Control (μ_C) folds is either greater than/equal to zero (≥ 0) or less than zero (< 0), as equivalently assessed using the following hypothesis-testing notations:

$$H_0 \text{ (null): } \mu_C \leq \mu_T, \text{ (i.e. } \Delta = \mu_T - \mu_C \geq 0 \text{) versus}$$
$$H_a \text{ (alternate): } \mu_C > \mu_T, \text{ (i.e. } \Delta = \mu_T - \mu_C < 0 \text{)}$$

For testing this hypothesis using the t distribution, H_0 will be rejected if the upper limit of the 95% confidence interval (CI) around Δ is < 0 using a one-sided p-value ($\alpha = 0.025$), otherwise H_0 will not be rejected.

Descriptive summary statistics for continuous variables will be presented for VAS pain assessments in Test and Control NLFs as well as for the difference between Test and Control i.e. (Test – Control).

7.1.2 Secondary Effectiveness Variables

Number and percentage of Merz NLF Scale responders at Week 6 will be presented for the Test and Control NLF sides. The p-value from McNemar's test comparing responses paired by subject will be presented to compare both percentages.

[REDACTED]

[REDACTED]

[REDACTED]

[REDACTED]

[REDACTED]

[REDACTED]

7.2 Safety Variables

All safety analyses will be performed on the SES.

AEs will be coded according to the Medical Dictionary for Regulatory Activities (MedDRA, version 20.0). Only treatment emergent adverse events (TEAEs) will be analyzed, which are defined as AEs with onset or worsening after the administration of the study drug. Incidences will be calculated for TEAEs on the system organ class level and on the preferred term level (total, by intensity, and by relationship – related or not related). Listings and tables displaying incidences for TEAEs leading to discontinuation and serious TEAEs will also be provided.

TEAEs associated with NLFs will be summarized by treatment. All TEAEs will be summarized without by-treatment breakdown.

In summaries by system organ class and preferred term each subject will be counted once per preferred term and treatment if applicable. Similarly in summaries by system organ class each subject will be counted once per system organ class and treatment if applicable. In summaries that are additionally broken down by intensity or relationship, subjects with multiple events will be summarized by the worst severity or worst relationship, as applicable.

Number and percentage of subjects with CTR, as well as the number of continuous CTR episodes, will be summarized by treatment and maximum severity as well as by treatment and maximum duration. Duration will be classified as 1-3 days, 4-7 days, 8-14 days 15-30 days and > 30 days.

7.3 Other Variables

Subject disposition, demographic characteristics and baseline characteristics will be presented using standard descriptive statistics for continuous variables (i.e. n, mean, SD, median, minimum, and maximum) and for qualitative variables (absolute and percent frequencies (i.e. n, %). Demographic and baseline characteristics will be summarized for the SES, the FAS, and the PPS.

Prior and concomitant treatments as well as non-pharmacological concomitant procedures will be listed. Prior and concomitant medications will be coded using WHO Drug Dictionary version Sept 2016 B2.

Frequencies of concomitant medications will be given based on different ATC code levels as well as by generic name for the SES. Indications for concomitant procedures will be coded and only listed. Medications will be considered prior of they have a stopping date that is prior to the first study injection. Medications that are ongoing or have stopped on or after the date of the first study injection will be considered concomitant.

Medical history and concomitant diseases will be summarized based on MedDRA (version 20.0) system organ class and preferred term levels for the SES. Medical history is defined as conditions that have a stopping date that is prior to the first study injection. Concomitant diseases are defined as conditions that are ongoing or have stopped on or after the date of the first study injection.

7.4 Special Statistical/Analytical Issues

7.4.1 Discontinuations and Missing Data

Imputation of effectiveness data

Observed Cases (OC)

- For the OC method, there will be no missing value imputations conducted. All effectiveness data will be analyzed as observed data.

Last Observation Carried Forward (LOCF)

- For the LOCF, in the analysis of the secondary effectiveness variable the subjects who have a missing score on the Merz NLF scale at Week 6 will have their latest available assessment (from the early discontinuation or unscheduled visit if available; failing

that, from the baseline visit) carried forward and imputed into the missing Week 6 assessment.

Imputation of safety data

For partial or completely missing start date of adverse events, the following imputation rules related to any treatment period will be used if applicable:

- If only the day is missing for any date used in a calculation, the 1st will be used to replace the missing day. If the new estimated date falls before the date of first dose, while the known month and year match the month and year of the first dose, the date of first dose will be used as the new estimated date.
- If the day and the month are missing, no estimation will be performed. However, if the year of onset is the same or greater than the year of the first dose date, the AEs will be considered treatment emergent and included in the summary tables.
- AEs with completely missing onset dates will be considered treatment emergent; no estimation of the dates will be performed.

Duration of CTRs would be computed using the following logic:

- Each subject is expected to have diary entries from Day 1 (day of the initial injection) up to and including Day 42 or the day of their completion/discontinuation, whichever comes first. If any subject does not have a diary entry for any of the required days, then for the purposes of CTR analysis it will be assumed that on the missing days they had all those CTRs (if any) that they had on the day before or on the day after the missing day, with the same severity.
- For any CTR with an uninterrupted single episode event, the duration will be computed as the days from the beginning of event to last date of event.
- For any CTR with multiple episodes, the CTR will be regarded as a continuous event if the date between paired episodes is not more than 1 day apart.
- For any CTR with multiple episodes, the CTR will not be regarded as a continuous event if the date between paired episodes is at least 2 days apart. In such instances, the duration with the longest duration will be used for that particular CTR.
- For any CTR with multiple continuous and not continuous events, the logic as aforementioned will be adopted, in which case the maximum of all CTR durations will be selected as the CTR duration to be used for summary purposes.

7.4.2 *Interim Analyses*

Not applicable.

7.4.3 *Data Monitoring Committee*

Not applicable

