Study subjects will receive treatment with Belotero Balance with integral lidocaine in one NLF (Test) and Belotero Balance without lidocaine in the contralateral NLF (Control) on Day 1. All subjects without ongoing, treatment-related, investigator-reported AEs will be eligible for an optional touch-up treatment, at the investigator's discretion and to achieve optimal correction, at Week 2. Each treatment session will consist of multiple mid- to deep-dermal injections of 0.1 to 0.2 milliliters (mL) Belotero Balance with and without lidocaine (up to a maximum of 3 mL per NLF over the two treatment sessions) into the left or right NLF according to the randomization assignment and the instructions for use. Subjects not receiving the optional, touch-up injection will be followed for six (6) weeks after their initial injection, while touch-up subjects will be followed for four (4) weeks after their last injection. Subjects will be evaluated at screening/enrollment, by phone at 72 hours after treatment, at Week 2 (optional touch-up treatment), and Week 6 (end of study). If subjects report a safety concern at the 72-hour phone call, an unscheduled visit will be scheduled to address safety concerns. Of the 52 estimated subjects enrolled, each NLF will be analyzed as a separate unit of measure (i.e., either Test or Control NLF) for the primary and secondary effectiveness endpoints, resulting in approximately 104 evaluable NLFs (52 Test, 52 Control). Pain levels, between the Test NLF and Control NLF, will be compared using a 10-cm VAS. Pain assessments will be evaluated at time zero (i.e., time the last injection needle is removed from each NLF, separately, after a full correction) [REDACTED].

Standard safety endpoints, including documentation of AEs and SAEs, will be assessed. Furthermore, several, pre-defined common treatment site responses (CTRs) will be evaluated via subject diaries.

Figure 1 illustrates the visit schedule associated with the split-face design. [Section 5.1](#) and [Appendix 11.1](#) detail a full schedule of study events and a schedule of events for each visit.

Figure 1: Study design

NLFs: Nasolabial folds; N: sample size; V: Visit; Wk: Week; R: Randomization; HR: hour

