- Administer Subject Pain-Preference Assessment (three questions) after treatment of both NLFs (i.e., immediately after the time-zero pain VAS assessment).

Additional visit 1 assessments:

- Record any AEs.
- Dispense subject diary and discuss completion instructions.
- Schedule 72-hour follow-up phone call.
- Schedule Visit 2.

Follow-up phone call (72-hours post treatment): Day 4 (\pm 1 day)

- Review and record changes in concomitant medications/procedures.
- Review and record any AEs reported by the subject.
- If subject reports a safety concern, arrange an unscheduled visit to address.
- Remind subject to record CTRs in the subject diary.
- Schedule and/or confirm Visit 2.

Visit 2 (Week 2): Day 14 (+ 3 days)

- Review and record any changes in concomitant medications/procedures.
- Review and record any adverse events.
- Review and collect subject diary. Record subject-reported CTRs in the eCRF. The investigator will review and initial the diary and determine if any entries should also be recorded as AEs on the AE eCRF.

For subjects receiving a touch-up injection at Week 2:

All subjects without ongoing, treatment-related, investigator-reported AEs are eligible for an optional touch-up treatment, at the investigator's discretion and to achieve optimal correction, at Week 2.

- Perform urine pregnancy test (if female of childbearing potential).
- Administer touch-up injection, **not to exceed the maximum allowable injection volume of 3 mL per NLF over the two treatment sessions (initial injection on Day 1 and optional touch-up injection at Week 2)**.
- Dispense subject diary and discuss completion instructions.

Visit 3 (Week 6): Day 42 (+ 3 days)

- Review and record any changes in concomitant medications/procedures.
- Review and record any adverse events.
- Perform urine pregnancy test (if female of childbearing potential).
- Take standardized NLF photographs.
- Have blinded evaluator independently perform the Merz Nasolabial Fold (NLF) Scale assessment.
 - **NOTE:** Every effort should be made to ensure that the same blinded evaluator perform the NLF scale assessment at both visits.
- [REDACTED]
- [REDACTED]
- [REDACTED]
- [REDACTED]
- [REDACTED]
- [REDACTED]
- Review and collect subject diary. Record subject-reported CTRs in the eCRF. The investigator will review and initial the diary and determine if any entries should also be recorded as AEs on the AE eCRF.

5.1.1 *Scheduled visits*

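### CTRs still present on the last diary day are tabulated as completed durations, so within the Day 42 diary period an unresolved CTR that starts at touch-up is reported as 15-30 days

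*SAP*

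**What the plan says.** SAP 6.2 lists this safety endpoint: "Incidence, severity, and duration of pre-specified CTRs reported in subject diaries". Protocol 2.2.4 lists the same one.

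SAP 7.4.1 sets the diary period. Day 1 is when the first injection is given, and the period then runs "up to and including Day 42 or the day of their completion/discontinuation, whichever comes first". For an uninterrupted single episode, "the duration will be computed as the days from the beginning of event to last date of event". The other rules in that section fill missing diary days from a neighbouring day, join episodes no more than one day apart, and take the longest duration when there are several. None of them addresses a CTR that is still being recorded when the diary stops.

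SAP 7.2 then groups the result: "Duration will be classified as 1-3 days, 4-7 days, 8-14 days 15-30 days and > 30 days". There is no class or row for a CTR that had not ended.

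Protocol 5.1 gives the visit timing: "Visit 2 (Week 2): Day 14 (+ 3 days") for the optional touch-up, and "Visit 3 (Week 6): Day 42 (+ 3 days") for the final visit, at which the diary is collected. Protocol 3.1 states the resulting follow-up: "touch-up subjects will be followed for four (4) weeks after their last injection".

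**The concern.** A duration that ends because the diary ends is a minimum, not a completed duration. Under the SAP rule, the last date of an unresolved CTR is simply the last diary day. It then enters the same class as a CTR that truly stopped on that day.

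Two groups are most exposed. One is CTRs that begin at the touch-up, where the remaining diary period is short. The other is CTRs in subjects who leave early.

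This matters because some listed responses can outlast a six-week study. The diary list in Protocol 3.2.2.1 includes firmness, lumps or bumps, and discoloration. Protocol 1.3 allows that induration, bumps, nodules and lumps may be permanent. As specified, the table gives a reader no way to tell how many responses were unresolved when observation stopped.

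**Working it through.** **Inputs.** Day 1 is the initial injection and diary entries are expected to Day 42 (SAP 7.4.1). Touch-up is on Day 14 to 17 and the final visit on Day 42 to 45 (Protocol 5.1). The top duration class is > 30 days (SAP 7.2).

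**Reproducing the plan's figure.** Day 42 − Day 14 = 28 days = 4 weeks, and Day 45 − Day 17 = 28 days. Both match the four weeks of follow-up after touch-up in Protocol 3.1.

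**Counting convention.** The SAP does not say whether both end days count, so both conventions are shown: subtraction (last − first) and inclusive (last − first + 1).

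**Unresolved CTR starting on the touch-up day, diary ending Day 42**

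| Touch-up day | Subtraction | Inclusive | Class |
|---|---|---|---|
| 14 | 28 | 29 | 15-30 days |
| 15 | 27 | 28 | 15-30 days |
| 16 | 26 | 27 | 15-30 days |
| 17 | 25 | 26 | 15-30 days |

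Onset later than the touch-up day shortens these figures further.

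**Latest onset that gives more than 30 days by Day 42.** Inclusive: 42 − s + 1 ≥ 31, so s ≤ 12. Subtraction: 42 − s ≥ 31, so s ≤ 11. Both fall before the first permitted touch-up day.

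**If entries from Day 43 to 45 count**

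| First day to last day | Subtraction | Inclusive |
|---|---|---|
| 14 to 43 | 29 | 30 |
| 14 to 44 | 30 | 31 |
| 14 to 45 | 31 | 32 |
| 15 to 45 | 30 | 31 |
| 16 to 45 | 29 | 30 |
| 17 to 45 | 28 | 29 |

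The > 30 day class is then reached in three combinations by inclusive counting and in one by subtraction, all with touch-up on Day 14 or 15.

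**CTR already present before touch-up.** The joining rule does not restart at the second injection. A CTR recorded continuously from Day 1 to Day 42 counts as 41 or 42 days and is classed as > 30 days, although not as a touch-up response.

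**Early leaver (illustration only).** A CTR present from Day 1 in a subject who withdraws on Day 6 counts as 5 or 6 days and is classed as 4-7 days, the same as one that resolved on Day 6.

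**The case against.** The strongest reply is that a persistent response has its own route. Protocol 7.1.8 asks the investigator to evaluate a non-resolving CTR as a possible AE. AEs carry start and stop dates (Protocol 7.2.4.1) and an outcome that can be recorded as not resolved (Protocol 7.2.3). An effort is made to follow unresolved ones past the final visit (Protocol 5.2.4), and Protocol 8.4.2.1 plans AE summaries by Test and Control that include duration. This stands, and it limits the problem to the CTR table. It does not repair that table. Protocol 3.2.2.1 leaves the investigator free not to report a CTR as an AE, and a CTR that is reported keeps its CTR duration. The AE tables specified in SAP 7.2 also contain no duration or outcome summary.

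A second reply is that the endpoint is duration as reported in diaries, and that the limit after touch-up comes from the declared design. That is fair: no analysis rule can lengthen follow-up. A rule can, however, mark which durations were cut off by it.

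Third, the diary form, eCRF and table shells are not among the documents, so an ongoing status might be captured there. That is possible. But SAP section 2 says the SAP is meant to guide the programming of the tables, and it gives no such instruction.

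Three stronger readings are tempting and are not supported:

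- **A touch-up response can never be reported as lasting more than 30 days.** The Day 42 sentence sets the expected entries and how gaps are filled. It does not say that later entries are dropped, and joined episodes can also exceed 30 days.
- **CTR durations are understated overall.** Gap filling, joining and use of the maximum push the other way, and the net effect is not shown. Only the unresolved CTRs are known to be recorded at a minimum.
- **The table favours one product.** Both folds belong to the same subject and share one observation period, so the cut-off falls on the same day for both.

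**Conclusion.** The concern holds in limited form. The SAP does not distinguish a CTR that ended from one still present on the last diary day, and it places both in the same duration classes.

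Taking Day 42 as the last diary day, an unresolved CTR that starts on the touch-up day is recorded as 25 to 29 days, always in the 15-30 day class. That result does not depend on the counting convention. It does depend on the CTR being new at touch-up and on Day 43-45 entries not being used, which the SAP leaves open.

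The number of subjects affected cannot be estimated. The documents give no expected touch-up rate, no rate of CTRs lasting to Week 6 and no rate of early withdrawal after treatment. It could be anywhere from none to all of the approximately 52 planned subjects.

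The primary and secondary effectiveness analyses are untouched, and no hypothesis test is planned on CTRs. The consequence is a descriptive safety table that can be misread as showing completed responses.

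**What to change.** In SAP 7.4.1:

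- Define a CTR present on the subject's last diary day as ongoing, and state that its duration is a minimum.
- Define the last diary day as the last day with an actual entry, before missing days are filled.
- State whether entries on Days 43 to 45 count, and whether duration includes both the first and the last day.

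In the SAP 7.2 table, report by treatment and CTR the number and percent ongoing at last entry, separately from the completed durations. Kaplan-Meier estimates are not needed for a descriptive table of this size.

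The diary data are already collected, so the change needs only SAP wording and programming before database lock. The cost is extra rows (11 listed CTRs × 2 products = 22 counts) and a duration table that looks slightly less favourable.
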